Apart from the main objective, we investigate the effects of the UP on emotion regulation, the role of possible mediators and moderators on outcome, as well as qualitative data on patients' and therapists' experience of psychotherapy. These analyses are specified elsewhere.

Study methods

Design

Please see study protocol (Arnfred et al., 2017)⁷ or www.clinicaltrials.gov (Identifier: NCT02954731).

Randomization

Please see study protocol (Arnfred et al., 2017)⁷.

Sample size

Please see study protocol (Arnfred et al., 2017)⁷.

Correction: In the study protocol we wrote that alpha was set to 5% resulting in a 95% one-sided confidence interval (CI). Following Trial guidelines^{1,8}, the alpha should be 0.025 resulting in a 97.5% one-sided CI. Further, standard deviation (SD) endpoint WHO-5 was reported to be 17.4 WHO-5 points. As reported in Reinholt et al. (2017)⁹ the correct WHO-5 endpoint SD is 20.44. Using these corrected values, then a sample size of 208 patients are required to be 90% sure that the lower limit of a one-sided 97.5% confidence interval (or equivalently a 95% two-sided confidence interval) will be above the non-inferiority limit of -9 WHO-points.

Due to an unexpected, high attrition rate within the first year of inclusion, we decided to adjust sample size calculations by increasing the number of included patients from in total 248 patients to in total 320 patients to get 204 participants completing the treatment as needed for the primary analysis based on our initial sample size calculations. The revised sample size calculation is documented in an amendment to the protocol at www.clinicaltrials.gov (Identifier: NCT02954731).

Timing of outcome assessments

Baseline characteristics will be assessed at the time of inclusion. Outcome measures will be assessed pre-treatment (up to two weeks before start of intervention), post treatment (week 19-21 after allocation), and at six months follow-up (45-47 weeks after allocation). The primary outcome (WHO-5) is further assessed at the beginning of each therapy session (14 sessions).

Timing of final analysis

Primary and secondary outcomes are analyzed post treatment and exploratively repeated at six months follow-up.

Statistical principles

Data presentation

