We will analyze and report primary and secondary outcomes in accordance with CONSORT reporting guidelines for non-inferiority and equivalence trials.² Results from the primary analysis will be reported as between group mean differences with one-sided 97,5% confidence intervals. The focus will be on hypothesis testing rather than point estimation. For secondary analyses, results will be reported as within and between group mean differences with one-sided 97,5% confidence intervals. Effect sizes (Cohens *d*) are calculated for each measure between groups. A one-sided p-value < .025 is considered significant. The focus of secondary analyses will be on point estimation rather than hypothesis testing.

No adjustment for multiplicity will be undertaken. Since outcomes are interrelated, adjustment will be overly conservative.

Adherence and protocol deviations

We will analyze attrition rates (number of patients receiving less than 8 sessions of therapy) in both groups using Chi-square analysis.

The analysis population

In superiority trials, the Intention-to-treat (ITT) analysis is considered the conservative choice to minimize possible type I-errors, that is falsely concluding that the one treatment is superior to another.¹⁰ The ITT population includes all patients randomized and allocated to treatment whether they violated the protocol or dropped out of treatment or not. In superiority trials, the null-hypothesis asserts that there is no difference between the two interventions being compared. The alternative hypothesis being tested is that the two treatments are different by some prespecified value.

A non-inferiority trial, conversely, tries to show that a new treatment is not unacceptably worse than the treatment used for comparison by a prespecified margin.^{11,12} The null hypothesis states that the new treatment is worse than the reference treatment by more than a prespecified non-inferiority margin. In non-inferiority trials, the ITT analysis is conventionally considered a liberal choice because it tends to make the two treatments being compared more similar, possibly falsely inflating type I-errors, that is concluding that the new treatment is non-inferior to the reference treatment. Following CONSORT reporting guidelines, the PP population is, therefore, considered the conservative choice of analysis in non-inferiority trials.²

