Given the potential biases in both PP and ITT analysis, the European Medicines Agency (EMA) in the paper *'Points to consider when switching between superiority and non-inferiority'* states that inference of non-inferiority should rely on both PP and ITT-analyses.⁸ Other authors (i.e. Sanchez & Chen, 2006¹³) argue that showing non-inferiority in both sets of analysis does not guarantee a valid conclusion as the conservatism or non-conservatism of the PP population depends on several factors, including the quality of the study, type of protocol violations and missingness. Sanchez & Chen (2006)¹³ recommend minimizing the impact of protocol violations and missingness in the statistical analysis by using a hybrid ITT/PP analysis which excludes non-compliant patients as in the PP population and properly addresses the impact of non-trivial missing data in an ITT analysis. We will use this hybrid model for analysis of primary and secondary outcomes.

For this analysis plan, the PP population is defined as patients completing the therapy (i.e. receiving eight therapy sessions or more). The ITT population is defined as all patients randomized and allocated to treatment.

Trial population

Eligibility

Please see study protocol (Arnfred et al., 2017)⁷ or www.clinicaltrials.gov (Identifier: NCT02954731).

Recruitment

Please see study protocol (Arnfred et al., 2017)⁷ or www.clinicaltrials.gov (Identifier: NCT02954731).

Participant flow

The number of patients screened, randomized, completed treatment, and completed follow-up outcomes, will be summarized in a CONSORT flow diagram.³

Baseline characteristics

The following demographic and illness burden variables will be summarized by treatment condition in Table 1: age, sex, immigrant status, marital status, level of employment, level of education, children living at home, comorbidity, previous psychological treatment, current medication, age of onset, previous episodes with primary diagnosis, previous hospitalization, and personality traits (Standardized Assessment of Personality Abbreviated Scale (SAPAS)).¹⁴

Analysis

Primary outcome

The primary outcome is self-reported subjective well-being measured with the WHO-5 assessed post treatment (19 weeks after allocation; single score continuous outcome).

Secondary outcomes

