The primary analysis will compare the estimated endpoint of the primary outcome (WHO-5) between UP and dCBT conditions post treatment (19 weeks from allocation) adjusted for baseline WHO-5 values, variables predictive for missing data, and stratification variables (i.e. site (Copenhagen, Risskov, Slagelse) and diagnosis (depression, social anxiety disorder, panic disorder/agoraphobia)), fitting treatment (UP or dCBT) as a fixed effects factor.

We will use a one-sided 97.5% CI interval approach to test non-inferiority between conditions. The one-sided 97,5% CI for the between group difference point estimate post treatment will be calculated. Non-inferiority of UP compared to dCBT will be accepted if the lower bound of the 97,5% CI lies within the prespecified non-inferiority margin of – 9 WHO points (see Figure 1). If non-inferiority is accepted, we will use a closed testing procedure to test for superiority of UP over dCBT (i.e. lower bound of the 97,5% CI lies above 0).

The model will be fitted using a multilevel, mixed linear regression model, which allow us to use all 16 WHO-5 outcomes and handle missing data within the model. We will use stratification variables (i.e. site and diagnosis) and baseline outcome variables and treatment as fixed factors. We will apply an unstructured covariance matrix to the random effects in the model. If the model does not converge, we will apply other covariance matrixes (i.e. autoregressive, heterogeneous, compound symmetry, etc.) to the model and choose the covariance matrix with the best fit according to the Akaike Information Criterion. Note: During the blind review of data it turned out that, due to the imputation method used, we were not able to run the analysis applying a unstructured covariance matrix to the random effects in the model as planned Using the Akaike Information Criterion, the autoregressive, 4th order (AR4) covariance matrix,

showed the best fit with the data. Accordingly, the multilevel, mixed linear regression model were run applying the AR4 covariance matrix to the random effects in the model.

Secondary analyses

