For secondary analyses we will use ANCOVA to test for non-inferiority between treatment conditions post treatment. Effect sizes (Cohens *d*) for pre-post differences between and within treatment conditions will be calculated. Following conventions (Cohen, 1988) statistically significant effect sizes ≤ 0.2 will be considered not clinically relevant and for this study a non-inferior difference between conditions.

All analyses will be run allowing for adjustment for stratification variables (i.e. site and diagnosis), and baseline values.

The clinically meaningfulness of results of study will be evaluated calculating numbers and odds ratio for responders and remitted patients using binary logistic regression. 'Responders' are defined as patients receiving a clinically meaningful change in primary outcome, that is ≥ 10 WHO-5 points 'Remission' is defined as patients no longer meeting diagnostic criteria for their primary DSM-5-diagnosis evaluated with the MINI Neuropsychiatric Interview (MINI)²³ 19 weeks after assessment. As an explorative analysis, we will also calculate numbers and odds ratio for patients who no longer met diagnostic criteria for any emotional disorder posttreatment.

Sensitivity analyses

We will run sensitivity analyses for the primary outcome using different definitions of the PP population, depending on how many therapy sessions they attended (i.e. 6, 10 sessions) and using the full ITT-population. Further, we will run a sensitivity analysis without imputed data to assess the potential impact of imputation on the trial findings and assess the impact of missingness by loading the primary analysis using an extreme scenario countering our hypothesis (i.e. imputing the data based on values from the 10% and 90% fractile population). Finally, we will assess the impact of nesting patients in therapy groups by adding therapy group as a random factor. As this analysis might unblind the analyst, this analysis is run after deciphering the blinding.

Additional analyses

Analysis of primary and secondary outcomes will be repeated exploratory at six months follow up.

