Adverse events will be listed by group and type of event: (a) Minor adverse events will be reported as number of patients encountering any of these: increasing current medication more than one standard dose step; using according-to-need medication for more than two weeks; increasing current medication to entail more than four types of psychotropic medications; new prescription of supplementary medication (accepted at inclusion); changing previously prescribed antidepressant to another type. (b) Major adverse events will be reported as number of events: New prescription of medication (not accepted at inclusion); contacting psychiatric emergency due to self-injury; suicide attempt without hospitalization; drop-out of therapy due to experienced lack of effect or deterioration. (c) Critical adverse events will be reported as number of events: psychiatric hospitalization due to deterioration or suicide attempt; somatic hospitalization due to self-injury or suicide attempt; referral to electroshock treatment; suicide.

Model checking and validation

We will check the robustness of models by examining residuals.

Handling of missing data and blinding

Data entry is performed by the data manager and research assistants according to the main study protocol. We will undertake a blinded analysis of missing data and outliers to evaluate how to deal with missing data and outliers, and to explore possible predictors of missing data which should be controlled for in the primary and secondary analyses. The analysis of the primary and secondary outcomes will be conducted with the treatment allocation blinded. In the data extraction for the primary analysis, the intervention type is concealed. The intervention and control arm will randomly be coded as '1' and '2'. Deciphering will not be done before all analyses at post-treatment have been performed, and conclusions for the primary outcome has been formulated.

For this analysis plan, we define missing data as those patients with the absence of data at follow-up for one or more outcomes. Data are assumed to be missing at random.

In the primary analysis, the mixed linear regression model handles missing data by full information maximum likelihood, except for the baseline value of WHO-5. Missing baseline WHO-5 values will be handled by multiple imputation with chained equations (m=100) using stratification variables, post-baseline values and variables predicting missing baseline WHO-5 as predictors in the imputation model.

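### The follow-on superiority test is decided in patients with at least 8 sessions, although the SAP itself names ITT as the conservative set for superiority

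*SAP*

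**What the plan says.** The SAP's Primary analysis section sets out two steps. Non-inferiority is judged first, from the one-sided 97.5% interval against a margin of -9 WHO-5 points. Then: "If non-inferiority is accepted, we will use a closed testing procedure to test for superiority of UP over dCBT", with success defined as the lower bound of that interval lying above 0. The superiority step has no analysis set or model of its own.

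The set comes from the section The analysis population. After describing a hybrid ITT/PP approach that removes non-compliant patients, the SAP says: "We will use this hybrid model for analysis of primary and secondary outcomes". It makes no exception for superiority. Per protocol means eight or more sessions. The Sample size section agrees, since recruitment was raised to 320 "to get 204 participants completing the treatment as needed for the primary analysis".

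The analysis population section also distinguishes the two aims. On superiority: "In superiority trials, the Intention-to-treat (ITT) analysis is considered the conservative choice to minimize possible type I-errors". On non-inferiority: "In non-inferiority trials, the ITT analysis is conventionally considered a liberal choice".

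The full randomised population appears under Sensitivity analyses, where the primary outcome is to be re-run with 6- and 10-session definitions "and using the full ITT-population", and with an extreme-scenario imputation. Under Adherence and protocol deviations: "We will analyze attrition rates (number of patients receiving less than 8 sessions of therapy) in both groups using Chi-square analysis".

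**The concern.** The SAP states which population guards against a false superiority claim and then tests superiority in a different one, without giving a reason. Its case for leaving ITT is that ITT can make two treatments look alike. That is a danger when the aim is non-inferiority, but it does not apply when the aim is to show a difference.

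Reaching eight sessions is an outcome of treatment, not a baseline characteristic. If drop-out depends on how patients are doing, and does so at different rates or to a different degree in the two arms, the completers are no longer comparable. Such drop-out is foreseen: under Adverse events the SAP lists "drop-out of therapy due to experienced lack of effect or deterioration" as an event type, though it gives no frequency, arm or timing.

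The bias could create a superiority finding or hide a real one. If the hybrid set showed superiority and the full ITT run did not, the rule as written would still declare superiority. The planned sensitivity analyses have no part in the decision. The chi-square test compares how many drop out in each arm, not who they are.

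**Working it through.** **Which set decides.** Superiority is read from the primary-analysis interval. That analysis is on the hybrid set without exception, and the hybrid set excludes patients with fewer than eight sessions. The SAP's own text therefore leads to superiority being tested in completers.

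**Inputs from the SAP.** 320 included, 204 expected completers, endpoint SD 20.44, one-sided alpha 0.025 (all from Sample size).

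**Assumptions.** 1:1 allocation (160 per arm), no true treatment difference, no covariate adjustment, and a normal latent attendance variable with correlation rho to the endpoint. The SAP gives no arm-specific drop-out and no rho. It also states no error rate for this step, so there is no figure of its own to reproduce.

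**Excluded share.** 1 - 204/320 = 36.25%, or 116 patients.

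**Shift of the completer mean in one arm.** SD × rho × m(p), where p is the drop-out share, m(p) = phi(z_p)/(1 - p), and phi(z_p) is the normal density at the p-quantile.

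- m(0.3625) = 0.3750/0.6375 = 0.588
- m(0.4125) = 0.3893/0.5875 = 0.663
- m(0.3125) = 0.3540/0.6875 = 0.515

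**False-superiority rate.** 1 - Phi(1.96 - d/SE), where d is the UP shift minus the dCBT shift. SE = 20.44 × sqrt(4/204) = 2.862 with equal drop-out. With 41.25% against 31.25% drop-out (94 and 110 completers), SE = 20.44 × sqrt(1/94 + 1/110) = 2.871.

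| Drop-out UP / dCBT | rho UP / dCBT | d (points) | Rate | Mirror case (dCBT more affected) |
|---|---|---|---|---|
| 36.25% / 36.25% | equal | 0 | 2.5% | 2.5% |
| 41.25% / 31.25% | 0.3 / 0.3 | 20.44 × 0.3 × (0.663 - 0.515) = 0.91 | 5.0% | 1.1% |
| 41.25% / 31.25% | 0.5 / 0.5 | 1.51 | 7.6% | 0.65% |
| 36.25% / 36.25% | 0.2 / 0 | 20.44 × 0.2 × 0.588 = 2.40 | 13.1% | 0.26% |
| 36.25% / 36.25% | 0.3 / 0 | 3.61 | 24.2% | 0.06% |

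Simulation of the four unequal cases (40,000 trials each) gave 5.3%, 8.3%, 13.4% and 24.8%. A separate grid, with a common rho of 0.2 to 0.5 and completion 5 to 15 points lower in UP, gave shifts of 0.3 to 2.3 points and rates from 3.2% to about 12%.

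**What ITT would give.** The same four cases were simulated with the full randomised set under different degrees of endpoint collection. One early score correlated 0.6 with the endpoint stands in for the session scores (8,000 trials per case in the three incomplete settings).

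| Endpoints of non-completers | False-superiority rate across the four cases |
|---|---|
| All observed | 2.5% to 2.8% |
| Half observed, plus early score | 2.6%, 3.2%, 4.2%, 6.0% |
| None observed, plus early score | 4.0%, 6.2%, 8.6%, 13.6% |
| None observed, no informative early score | 4.9%, 8.6%, 13.8%, 24.8% |

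The last row is no better than the completer set. The gain from ITT depends on how many endpoints are collected and on how informative the session scores are.

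**The case against.** The strongest reply is that this is a gap in labelling, not a missing analysis. The full-ITT run, the alternative session cut-offs and the extreme-scenario imputation are all prespecified, so a superiority result confined to completers would be visible. That is true, but visibility is not a decision rule: nothing says what follows when the sets disagree.

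Second, the inflation figures rest on assumed selection. Nothing in the SAP suggests that drop-out is tied to outcome in one arm and not in the other, which is what the 13.1% to 24.2% cases require. This stands. Those figures are illustrations, and the error may equally fall below 2.5%.

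Third, ITT is no cure if patients who stop also lack the endpoint. This also stands, as the second table shows, and the remedy should not be presented as restoring 2.5% in general.

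Fourth, the case for the hybrid set starts from possible bias in both ITT and PP, so it is not purely about direction. Its conclusion, however, concerns the validity of a non-inferiority claim.

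Fifth, the model adjusts for baseline WHO-5, site, diagnosis and predictors of missingness. That can absorb selection acting through those variables but not selection on response to treatment. The mixed model handles missing scores of included patients and cannot bring back those excluded.

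Finally, superiority is a conditional step in a trial designed for non-inferiority. That limits the weight of the point but does not remove it.

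**Conclusion.** The concern holds and should be fixed. The superiority claim is assigned to a completer set that the SAP's own reasoning does not support for that purpose, with a planned 36% of patients outside it. That conclusion rests on the text alone.

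The size of any distortion cannot be known from the SAP. It is nil with equal drop-out and equal selection in both arms. In the assumed unequal cases the nominal 2.5% becomes anything from 0.06% to 24.2%, depending on the direction and strength of selection, with SD 20.44, 1:1 allocation and no covariate adjustment. The non-inferiority conclusion and its choice of population are outside this point.

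**What to change.** Add to the Primary analysis section:

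> If non-inferiority is accepted in the hybrid set, superiority is tested in the full ITT population (all patients randomised and allocated) with the same mixed model, and is concluded if the lower 97.5% bound lies above 0. The hybrid-set result is supportive.

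State beside it that this result relies on the missing-at-random assumption made under Handling of missing data and blinding, because patients who stop early lack later session scores and may lack the endpoint. Report the planned extreme-scenario imputation next to the ITT result.

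The cost is one or two sentences. The ITT run is already planned. The fixed order, non-inferiority and then superiority at one-sided 2.5%, still needs no alpha adjustment, and the non-inferiority population stays as chosen. The price is a heavier reliance on missing at random, and possible dilution of a true difference by patients who received little treatment. The Primary analysis section shows that modelling had begun during the blind review, so the change has to be registered before the blind is broken, which the Introduction allows.

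### The fixed effects listed for the primary mixed model include no visit or treatment-by-visit term, so they cannot deliver the week-19 WHO-5 difference that the SAP declares

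*SAP*

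**What the plan says.** **The target.** Under Primary outcome, the SAP defines WHO-5 as "assessed post treatment (19 weeks after allocation; single score continuous outcome"). Under Primary analysis it states the comparison in these words: "The primary analysis will compare the estimated endpoint of the primary outcome (WHO-5) between UP and dCBT conditions post treatment (19 weeks from allocation"). The same section gives the decision quantity: "The one-sided 97,5% CI for the between group difference point estimate post treatment will be calculated". Its lower bound is set against −9 for non-inferiority and then against 0 for superiority.

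**The model.** Primary analysis then specifies a multilevel mixed linear regression, "which allow us to use all 16 WHO-5 outcomes and handle missing data within the model". The terms of the mean are given twice. The first statement has the comparison "adjusted for baseline WHO-5 values, variables predictive for missing data, and stratification variables", with treatment as a fixed effect. The second is "We will use stratification variables (i.e. site and diagnosis) and baseline outcome variables and treatment as fixed factors". After the blind review, "the multilevel, mixed linear regression model were run applying the AR4 covariance matrix to the random effects in the model".

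**The occasions.** Timing of outcome assessments schedules WHO-5 before treatment, after treatment and at six months. It adds: "The primary outcome (WHO-5) is further assessed at the beginning of each therapy session (14 sessions"). Handling of missing data and blinding says that full-information maximum likelihood covers missing WHO-5 values except at baseline, which is multiply imputed.

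**Interactions.** The only ones named anywhere, under Subgroup analysis, are with site and diagnosis.

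**The concern.** The target is one time point, but the model is fitted to many. If treatment is the only term that separates the arms, the model forces the same difference on every response occasion and estimates it from all of them. That includes session 1, where WHO-5 is completed before any therapy has been given. The resulting interval belongs to an average over the course of treatment and not to week 19.

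This is the trial's only confirmatory test. If the arms separate gradually, averaging dilutes a real week-19 deficit and non-inferiority is accepted too often. If an early deficit recedes, the bias shrinks or reverses. If the difference is constant, there is no bias. The SAP does not state or justify a constant difference.

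**Working it through.** **1. Terms needed and terms given.** A week-19 difference from a repeated-measures model needs a treatment effect that can vary by occasion: treatment-by-visit, or an equivalent. The terms given are treatment, baseline, site, diagnosis and predictors of missingness. A visit main effect alone would not help, because it moves both arms together. AR4 describes correlation and adds nothing to the mean. The analyses under Sensitivity analyses vary the population, the imputation and the clustering, but not the mean model.

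**2. What the single coefficient estimates.** Let *d_k* be the true difference at occasion *k* and *R* the working correlation matrix. The coefficient estimates Σ *w_k d_k*, with *w* = *R*⁻¹**1** / (**1**′*R*⁻¹**1**). Take 15 responses (14 sessions and post treatment) and linear divergence from session 1, so *d_k* = −9(*k* − 1)/14. Independence, compound symmetry and AR(1) at 0.5, 0.8 and 0.9 all give a factor of 0.50, by symmetry of the weights, so the coefficient is −4.5. If divergence begins only in the second half, the factor is 0.30–0.41. For a constant difference it is 1.

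**3. Consequence at the margin.** Let the averaged difference be *r* times a true week-19 deficit of −9. The probability that the lower bound exceeds −9 is then Φ(9(1 − *r*)/SE − 1.96). The SE of the averaged coefficient is not in the SAP; the simulations in step 4 give 1.5–1.7.

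| *r* | SE 1.7 | SE 1.5 |
|---|---|---|
| 1 | Φ(−1.96) = 2.5% | 2.5% |
| 0.9 | Φ(0.9/1.7 − 1.96) = 7.6% | Φ(0.9/1.5 − 1.96) = 8.7% |
| 0.75 | Φ(2.25/1.7 − 1.96) = 26% | Φ(2.25/1.5 − 1.96) = 32% |
| 0.5 | Φ(4.5/1.7 − 1.96) = 75% | Φ(4.5/1.5 − 1.96) = 85% |

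The direction does not depend on the small SE. With a single-endpoint SE of 20.44 × √(4/208) = 2.83, linear divergence still gives about 32%–39%, for *r* between 0.53 and 0.47 (the range across the possible sets of response occasions).

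**4. Simulation.** From the SAP (Sample size): 204 patients, taken as 102 per arm, and SD 20.44. Assumed: a 15-point improvement common to both arms, and a random intercept plus AR(1) errors with (intercept share, autocorrelation) of (0.3, 0.7), (0.5, 0.5) or (0.2, 0.8). There were 15 responses, baseline as covariate, AR(4) residuals and 1,500 trials per setting; site, diagnosis and missingness predictors were left out. The true week-19 difference is −9 throughout, so acceptance should be 2.5%.

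| Course of the difference | Terms as listed | Plus visit main effect |
|---|---|---|
| Linear divergence | 77%–87% | 78%–87% |
| Plateau by session 8 | 44%–57% | 45%–58% |
| Plateau by session 5 | 32%–37% | 34%–38% |
| Full deficit from session 2 | 19%–21% | 20%–21% |
| Early peak of −13.5, receding | 9%–11% | 10%–12% |
| Early peak of −18, receding | 1.5%–1.7% | 1.6%–2.1% |
| Constant −9 | 1.5%–2.4% | 1.7%–2.7% |

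With treatment-by-visit and the week-19 contrast, acceptance was 1.9%–4.5% under AR(4). The contrast's model SE in the (0.2, 0.8) structure was 2.60, against an empirical SD of 2.8–3.0. Under unstructured covariance and linear divergence, acceptance was 1.9%–2.4%.

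**5. Occasions.** Scheduled: 1 + 14 + 1 + 1 = 17. Used: 16. Pre + 14 + post gives 16 and is the natural reading. With baseline as covariate only, which fits the missing-data section, 15 responses remain. The text also allows baseline as both response and covariate; in that case even a constant post-baseline difference is recovered at only 71%–94% (same correlation assumptions as step 2). Including the six-month score (14 + 1 + 1 = 16) is less plausible, because follow-up is an exploratory repeat.

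**The case against.** The strongest reply is that the SAP does state its target, twice, and that an analyst who reported a session-averaged coefficient would contradict it. The list of fixed factors is visibly shorthand, since it omits the missingness predictors named just before it. An unstructured or AR4 covariance also needs an ordered occasion index, so occasion must have been in the set-up in some form. On this view the text is incomplete and the analysis is not shown to be wrong.

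Part of this stands. The intention is clear, and the fitted model may have contained more than the text lists. But intention does not identify a coefficient. This is the section that specifies the primary model, and it does not defer to the protocol on the point. Ordering occasions for the covariance puts no treatment-by-visit term in the mean.

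Two further objections hold in part. The acceptance rates run from 1.5% to 87% according to assumed time courses, so they illustrate what could happen and do not predict this trial's error rate. The question of which occasions are responses is a secondary clarification: the number is given, and one reading is clearly the most natural.

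**Conclusion.** The concern holds and should be corrected before the blind is broken. As written, the mean model can place a session-averaged difference against −9 and 0, while the SAP declares a week-19 difference. The two coincide only if the arm difference is constant over the response occasions.

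The absence of the terms is a matter of text and is certain. Whether the fitted model also lacked them cannot be told from the SAP. The size rests on assumed trajectories and correlations: from no inflation with a constant or strongly receding difference to false acceptance in most trials under linear divergence. Even a 10% dilution (*r* = 0.9) roughly triples the nominal 2.5%, given an SE of 1.5–1.7.

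**What to change.** Amend Primary analysis as follows:

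- List the responses as the 14 session scores and the post-treatment score, with baseline as covariate only.
- Add visit (categorical, or another stated form of time) and treatment-by-visit as fixed effects.
- State that the interval compared with −9, and then with 0, is that of the treatment contrast at the post-treatment visit.
- Name the six-month contrast for the exploratory repeat.
- Re-select the covariance structure under this mean model. This step is essential: AR4 was chosen without these terms in the stated model, and the week-19 contrast can be somewhat anti-conservative under it. The SAP reports that the imputation method prevented an unstructured fit, so the amendment should say how the choice is made if that remains so.

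**Cost.** No new data are needed. The blind review is done and the AR4 model has been run, but the Introduction leaves the SAP open to adjustment until unblinding. If the terms were already fitted, stating them takes a sentence.

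The price is a wider interval. Under the simulation's assumptions and complete data, the SE rises from about 1.5–1.7 to 2.4–2.6 (AR4) or 2.6–2.9 (unstructured). Power at a true difference of zero is then 91%–95% or 86%–96%. The SAP's own SD with 102 per arm implies 20.44 × √(2/102) = 2.86, so with complete data this is about the precision the design assumed. With assumed drop-out after session 8 and an unstructured covariance, power is 86%–93% at 10% drop-out and 80%–89% at 25%. The latter falls short of the planned 90%.
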